The 21 subjects reporting Grade 4 treatment-related TEAEs experienced events of infusion-related reaction (3 subjects; 0.2%), blood CPK increased, GGT increased, hyperglycemia (2 subjects each; 0.2%), lipase increased, amylase increased, myositis, hypophosphatemia, hypokalemia, embolic stroke, frontal lobe epilepsy, monoplegia, syncope, dyspnea, pneumonitis, respiratory failure, anemia, neutropenia, thrombocytopenia, autoimmune neutropenia, sepsis, cardiac arrest (1 subject each; 0.1%), and 1 uncoded event. The 4 subjects with Grade 5 treatment-related TEAEs

experienced events of radiation pneumonitis, pneumonitis, respiratory distress and acute hepatic failure, autoimmune hepatitis (Grade 3) with consequent fatal liver failure. Infusion-related reactions including drug hypersensitivity reactions and immune-mediated adverse reactions have been identified as expected adverse drug reactions of avelumab. The safety profile of avelumab is consistent with findings reported for other anti-PD-1 or anti-PD-L1 antibodies.

Immune-related adverse event (irAEs) are considered AE's of special interest. Treatment-related potential irAEs were observed in 99 of 1300 subjects (7.6%) in the pooled expansion cohort. Hypothyroidism was the most frequent treatment-related potential irAE, which occurred in 45 subjects (3.5%) in the pooled expansion cohort. The other frequent potential irAEs, which were considered as treatment-related, were pneumonitis (13 subjects; 1.0%), hyperthyroidism (7 subjects; 0.5%), adrenal insufficiency and dry eye (5 subjects each; 0.4%), autoimmune hepatitis and colitis (4 subjects each; 0.3%), and myositis (3 subjects; 0.2%). Additional treatment-related potential irAEs were seen in 2 or 1 subjects in the pooled expansion cohort. The majority of potential irAEs were Grade 1 or Grade 2 events. In the pooled expansion cohort, potential irAEs  $\geq$  Grade 3 occurred in 29 (2.2%) subjects. Potential irAEs leading to death occurred in 3 (0.2%) subjects, which were all assessed as treatment-related events. In the pooled expansion cohort, 15 subjects (1.2%) had potential irAEs that led to trial treatment discontinuation. Overall, as of 05 November 2015, there were no treatment-related immune-mediated AEs reported in Trial EMR 100070-001 with onset after the on-treatment period, i.e., 30 days after the last drug administration.

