## Assessment and Initial Management of Tumor Lysis Syndrome

## 11.6. Immune related Adverse Event (irAE)

Immune checkpoint inhibitors are known to cause autoimmune adverse events. Previous studies with avelumab has shown an incidence of 9.7% most of them of grade 2 severity.

Any untoward medical occurrence, sign/symptom, disease, including laboratory abnormality or exacerbation of previous condition occurring during the study drug and believed to be of autoimmune origin will be classified as an immune related/emergent autoimmune adverse event (irAE).

Treatment of irAE's is mainly dependent upon severity (NCI-CTCAE grade):

Grade 1 to 2: treat symptomatically or with moderate dose steroids, more frequent monitoring

Grade 1 to 2 (persistent): manage similar to high grade AE (Grade 3 to 4)

Grade 3 to 4: treat with high dose corticosteroids

Treatment of irAEs should follow guidelines set forth in the table below (table 3).

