1. STATISTICAL STATEMENT AND ANALYTICAL PLAN

1.1. Sample Size Considerations

A convenience sample of thirty (30) patients is based on recruitment feasibility. This sample size will permit estimation of dichotomous outcome rates with margins of error of less than 18% (based on a significance level of 0.05) and estimation of continuous parameter means to within 0.36 standard deviations. This is an early stage study, so analysis will focus on descriptive statistics. Continuous parameters will be summarized by means and 95% confidence intervals or by medians and interquartile ranges, as appropriate. Dichotomous outcomes will be summarized with point estimates of the rate, as well as 95% confidence intervals. Time-to-event data will be summarized using Kaplan-Meier curves.

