1.3.2. Secondary Endpoints

Based on the results of Stupp *et al* (2005) (3), if avelumab had no effect then we would expect to see one-year overall survival and progression-free survival rates of 60% and 27%, respectively. We will conclude that we have preliminary evidence of benefit if either of our observed rates is significantly better based on a one-sided t-test at the 0.2 level of significance. With our projected sample of 30, this corresponds to concluding benefit if at least 21 patients survive to one-year or if at least 11 have survived without progression of disease.

Radiological tumor response will be graded according to the immunotherapy Response Assessment for Neuro-Oncology (iRANO)

Progression of Disease (PD) will be defined as a $\geq 25\%$ increase on the 12 month MRI or CT scan in the sum of the product of the biperpendicular diameters of enhancing disease; or new lesions; or substantial worsened T2/FLAIR; or significant clinical neurological decline unexplained by a change in medication or concurrent comorbidities. The SPD is the sum of the products of biperpendicular diameters of the measurable enhancing lesions (max 5 lesions).

Complete Response (CR) will be defined as the disappearance on the month 12 MRI or CT scan of all enhancing disease, no new lesions, with stable or improved T2/FLAIR; no more than physiological steroids; clinically stable or improved

Partial Response (PR) will be defined as a $\geq 50\%$ decrease on the month 12 MRI or CT scan in the sum of the product of the biperpendicular diameters of enhancing disease, no new lesions, stable or improved T2/FLAIR, stable (>2 months) or decreased steroid dose, clinically stable or improved

Stable Disease (SD) will be defined at 12 months when a patient do not qualify for complete response, partial response, or progressive disease, stable or improved T2/FLAIR; stable (>2 months) or decreased steroid dose, clinically stable or improved

Overall survival (OS) will be defined as the time from baseline to the date of death from any cause.

Objective Response Rate (ORR) will be defined the number of patients with either CR or PR divided by the total number of patients.

Progression Free Survival (PFS) will be defined as the time from baseline to documented PD or death from any cause.

Results will be stratified according to MGMT status, baseline age (>50 yrs), baseline Karnofsky performance score (score of 100), radical tumor resection vs biopsy, primary versus secondary GBM,

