1.3.3. Exploratory

The incidence of PD-L1 expression on tumor cells and microglia/macrophages within the tumor will be determined and correlated to OS and PFS and other iRANO endpoints

The histological immunoscore will be determined and tested for association with OS, PFS, and other iRANO endpoints using logistic regression.

The association between 12 months OS and PFS with baseline neurocognitive function as measured by the evoked potential P300 (normal), the baseline corticosteroid dose, the average daily corticosteroid dose over the whole study duration, the extent to which patients complete the full 6 cycles of temozolomide based on temozolomide toxicity and the incidence and severity of treatment related irAE's will be tested using logistic regression.

The change if any in histological markers on tissue obtained from repeat resection

The estimation of the time period in which radiological progression was seen in clinically stable patients whose imaging was subsequently followed by radiological stabilization or regression

The estimation of the time period in clinically stable patients before radiological evidence of tumor regression occurred

The change in P300 will be determined and correlated with clinical outcomes as per iRAN

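### If immune-related events are as rare as in the earlier avelumab studies, the planned logistic regression has no finite odds ratio for them in roughly 40-60% of trials of this size; a penalised or exact analysis should be named instead.

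*SAP*

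**What the plan says.** SAP 1.3.3 lists several exploratory predictors of 12-month OS and PFS. The last is immune-related events, for which "the incidence and severity of treatment related irAE's will be tested using logistic regression". Protocol 12.3.3 has the same sentence, and protocol 3.3 lists the question among the exploratory objectives.

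On sample size, SAP 1.1 states: "A convenience sample of thirty (30) patients is based on recruitment feasibility". On irAE frequency the protocol gives two figures. Section 2 reports: "Treatment-related potential irAEs were observed in 99 of 1300 subjects (7.6%) in the pooled expansion cohort". Section 11.6 reports: "Previous studies with avelumab has shown an incidence of 9.7% most of them of grade 2 severity". For severe potential irAEs, section 2 says that those of at least "Grade 3 occurred in 29 (2.2%) subjects". SAP 1.3.2 takes as its no-effect reference "one-year overall survival and progression-free survival rates of 60% and 27%, respectively".

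For this analysis neither document mentions sparse data, separation, an exact or penalised method, a minimum number of events, or a fallback. Neither says whether the predictors enter one model or several, which test statistic is meant, or how severity is coded.

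**The concern.** A logistic regression estimates a finite odds ratio for a yes/no predictor only if both outcomes occur among patients with the predictor and among those without it. With two or three irAE patients in 30, it is quite likely that all of them are alive, or all dead, at 12 months. The likelihood then keeps rising as the coefficient goes to plus or minus infinity. Standard software stops at an arbitrary large coefficient with an enormous standard error, and its Wald p-value is close to 1.

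What is at stake is a misleading answer to a stated exploratory question. A reader could see an apparent lack of association, or an absurd odds ratio, in data where every irAE patient had the same outcome. If the method is changed only after the model has failed, the change is made with the data in view.

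**Working it through.** **The plan's own figures.** The documents give no figure for this regression. The general precision statement for n = 30, "margins of error of less than 18% (based on a significance level of 0.05", reproduces: 1.96 × √(0.25/30) = 0.179. So does the 0.36 SD for a mean: 1.96/√30 = 0.358.

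**Inputs.**
- n = 30 (SAP 1.1).
- irAE rate π = 99/1300 = 7.6% (protocol 2) or 9.7% (protocol 11.6).
- 12-month rate q = 60% for OS and 27% for PFS (SAP 1.3.2).
- Assumption: irAE and outcome are independent.

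**Expected irAE patients.** 30 × 0.076 = 2.28; 30 × 0.097 = 2.91.

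**Formula.** Let K be the number with an irAE, K ~ Binomial(30, π). No finite odds ratio exists if K = 0, or if all K patients share one outcome, which has probability q^K + (1−q)^K. The chance of an empty cell among patients without an irAE is included but negligible.

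For OS, q^K + (1−q)^K is 1 at K = 1, 0.52 at K = 2, 0.28 at K = 3, 0.155 at K = 4 and 0.088 at K = 5. At π = 7.6%:

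0.093 (K = 0) + 0.230 × 1 + 0.275 × 0.52 + 0.211 × 0.28 + 0.117 × 0.155 + 0.050 × 0.088 + about 0.001 (K ≥ 6) = 0.55.

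| irAE rate | No irAE at all | OS: separated | OS: no finite OR | PFS: separated | PFS: no finite OR |
|---|---|---|---|---|---|
| 7.6% | 9.3% | 45.6% | 55% | 53.1% | 62% |
| 9.7% | 4.7% | 37.7% | 42% | 46.8% | 51% |

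A simulation with a linear-programming separation check (3,000 runs per scenario) gave 55% and 64% (OS, PFS) at 7.6%, and 42% and 51% at 9.7%.

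**Both models together.** Every progression-free patient is alive, so the chance that both models fail given K ≥ 1 is 0.27^K + 0.33^K + 0.40^K. Summed over K, at least one of the two models fails with probability 72% (7.6%) or 62% (9.7%).

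**Sensitivity to the irAE rate (assumed values).**

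| irAE rate | OS | PFS |
|---|---|---|
| 12% | 31% | 42% (0.415) |
| 15% | 21% | 31% |
| 20% | 10% | 20% |
| 30% | 2% | 8% |

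**Sensitivity to the outcome rate.** With one-year OS of 70% the figures are 60% (irAE 7.6%) and 49% (9.7%). With 12-month PFS of 11/30 they are 56% and 44%.

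**Sensitivity to independence.** If irAE patients had 80% one-year survival, the OS figures would be 69% and 60%. If they had 50%, 53% and 40%.

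**Severity.** If severity were split at Grade 3 or higher (an assumed coding), the rate is 29/1300 = 2.2%, with 30 × 0.022 = 0.66 patients expected. The probability of no finite odds ratio is then 93% (OS) and 94% (PFS). If grade were an ordered score with 0 for no irAE, the coefficient is infinite just when all irAE patients share one outcome, so the figures are those for any irAE.

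**What separation does to the output.** Take 3 irAE patients, all dead at one year, and 18 of 27 others alive.
- Ordinary fit: log odds ratio about −22.3, standard error about 16,900, Wald p = 0.999.
- Likelihood-ratio test: the null log-likelihood is 18 ln 0.6 + 12 ln 0.4 = −20.19. The alternative is 18 ln(2/3) + 9 ln(1/3) = −17.19. Twice the difference is 6.0, p = 0.014.
- Score test: 30 × (3 × 18)²/(3 × 27 × 18 × 12) = 5.0, p = 0.025.
- Fisher's exact test: C(12,3)/C(30,3) = 220/4060, p = 0.054.
- Firth estimate (half added to each cell): (0.5 × 9.5)/(3.5 × 18.5) = 0.073, which is finite.

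**The case against.** The strongest objection is that a non-finite odds ratio is not a failed test. The SAP says that the association will be tested, and it does not prescribe Wald tests. The example above shows that likelihood-ratio, score and exact tests remain defined under separation. A reader might infer that the planned test usually cannot be computed. That does not follow: the test itself is lost only when no irAE occurs, in 9% of trials at 7.6% and 5% at 9.7%. Even for the odds ratio, a finite OS estimate is the more likely result at 9.7%. This objection stands.

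The irAE rates are also imported. The 7.6% comes from the pooled expansion cohort of a phase I trial, and the 9.7% only from previous studies. Here avelumab is added to temozolomide, dosing may run to 260 weeks, and section 11.6 defines an irAE broadly. The rate could differ, although the documents give no other figure to plan on. So the result must be stated as conditional on the rate.

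A reader might also infer that severity necessarily fares worse than incidence. The plan does not split severity at Grade 3, so this is not shown.

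Finally, any method is nearly uninformative with two or three affected patients. Firth's method cannot help when no irAE occurs, and an exact interval under separation is open on one side. That is true, but it does not defend printing a meaningless estimate. The choice costs nothing if made in advance.

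**Conclusion.** The concern holds in conditional form. At the irAE rates the protocol itself cites, and assuming no association, ordinary logistic regression gives no finite odds ratio for irAE in 42-55% of trials for 12-month OS and 51-62% for PFS. The few percent in which no irAE occurs are included. In the separated trials the odds ratio and Wald p-value should not be reported.

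The irAE rate drives the result; the outcome rates matter much less. The conclusion does not depend on whether predictors are modelled singly or jointly, which the SAP leaves open. A simulated model with five predictors (three normal, one binary at 40%, and irAE; all assumed) failed at similar rates: 55% and 66% for OS and PFS at 7.6%, 42% and 52% at 9.7%.

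The consequence is confined to one exploratory analysis in a plan that puts descriptive statistics first. It touches neither the primary safety endpoint nor the secondary benefit rule of "at least 21 patients survive to one-year or if at least 11 have survived without progression of disease".

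**What to change.** In SAP 1.3.3 and protocol 12.3.3, replace ordinary logistic regression for irAE as follows:
- Use Firth-penalised logistic regression with profile penalised-likelihood intervals, one predictor at a time. Alternatively, use Fisher's exact test with an exact interval, noting that the interval may be one-sided.
- Always show the 2x2 counts of irAE by 12-month outcome, for OS and for PFS.
- If no irAE occurs, state that the association is not estimable.
- Report severity descriptively, by a listing of each irAE patient with grade and outcome, without a test.

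The cost is a few sentences of SAP wording and a standard software option. Penalised estimates shrink slightly toward no effect, and intervals will be wide under any method.
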